4.4 FOLLOW-UP PHASE

The duration of follow-up depends on whether subject experiences treatment failure.

- Subjects who experience treatment failure within Treatment Phase Part 2 will be followed up every 4 weeks until viral suppression is achieved (i.e., plasma HIV-1 RNA levels below level of detection) or up to a maximum of 6 months after cessation of therapy if the treating physician does not feel that there is an antiretroviral regimen that will regain full viral suppression.
- Subjects who do not experience treatment failure at the end of Treatment Phase Part 2, will be followed up every 2 weeks for total of 4 weeks.

4.4.1 Follow-Up Visits

The following assessments will be performed at each follow-up visit, unless otherwise specified:

- Assess for any Adverse Events and changes in Concomitant medications (see [section 9](#) and [7.5](#)),
- Symptom-directed physical examination (see [section 7.7](#)),
- Vital Signs (see [section 7.10](#)),
- Collection of Blood Specimens (see [section 7.11](#)) for
 - Plasma HIV-1 RNA level
 - TruCount T Assay
 - Anti-idiotypic antibodies to PRO 140 (only at Treatment Failure - FU1 and Non Treatment Failure - FU2)

4.5 UNSCHEDULED VISITS

In the event that the patient returns to clinic at a time other than a regularly scheduled study visit, the visit will be regarded as an unscheduled visit. Assessments at unscheduled visits are at the discretion of the Investigator.

5 SUBJECT COMPLETION AND WITHDRAWAL

5.1 SUBJECT COMPLETION

- A subject who completes Treatment Phase Part 2 (without treatment failure) and 4- week Non-Treatment Failure Follow-Up Phase will be considered as having completed the study.
- A subject who experiences treatment failure during the Treatment Phase, undergoes the Treatment Failure (TF) Visit assessments and is followed up until viral suppression is achieved or up to a maximum of 6 months after experiencing treatment failure if the treating physician does not feel that there is an antiretroviral regimen that will regain full viral suppression will be considered as having completed the study.

5.2 SUBJECT WITHDRAWAL

A subject who enters the Treatment Phase but does not complete the study, as defined in [Section 5.1](#), is considered to have prematurely withdrawn from the Study.

All subjects have the right to withdraw at any point during treatment without prejudice to future care. It will be documented whether or not each subject completed the clinical study. If for any subject, study treatment or observations were discontinued, the reason(s) will be recorded.

The Investigator can discontinue a subject at any time if it is considered medically necessary.

In addition, subjects WILL be withdrawn from the study, in consultation with the MedicalMonitor and the Investigator, if any of the following are met:

- A subject is significantly non-compliant with the requirements of the protocol.
- The investigator determines that it is in the best interest of the subject.
- Subject chooses to withdraw or is withdrawn due to an adverse event
- A subject becomes pregnant

Note: *The pregnancy will be followed to term for safety follow-up. Relevant safety information collected after the study has completed will be reported as supplemental information.*

- Discontinuation of study by Sponsor

Premature withdrawal from the study MAY occur if, in consultation with the Medical Monitor and the Investigator, any of the following are met:

- A subject is treated with a prohibited medication.

- Major protocol violation

5.2.1 Discontinuation of Study Treatment

Discontinuation of study treatment (PRO 140) and continuation of HAART as per standard of care is recommended if:

- Subject experiences treatment failure

Defined in terms of virologic non-response and virologic rebound in the Open-Label Treatment Phase (Part 2) of the study:

(1) Virologic non-response is defined as two consecutive viral load results of:

- $<0.5 \log_{10}$ copies/mL decrease in HIV-1 RNA at Day 7 of Treatment Phase Part 2. [Assessment Timepoint: T3 visit]
- $<1 \log_{10}$ copies/mL decrease in HIV-1 RNA at or after Week 4 of Treatment Phase Part 2 unless HIV-1 RNA <400 copies/mL. [Assessment Timepoint: from T6 up to T25 visit]
- Confirmed plasma HIV-1 RNA levels ≥ 400 copies/mL at Week 24 of Treatment Phase Part 2. [Assessment Timepoint: T25 visit]

(2) Virologic rebound is defined as two consecutive viral load results of:

- $\geq 1.0 \log_{10}$ copies/mL increase in plasma HIV-1 RNA above nadir level* in Treatment Phase Part 2 [Assessment Timepoint: from T3 up to T25 visit] or

**Note: This refers to “Nadir” level in Treatment Phase Part 2 which starts from T2 visit*

- ≥ 400 copies/mL after suppression to <50 copies/mL in Treatment Phase Part 2. [Assessment Timepoint: from T3 up to T25 visit]

Note: Subjects will be allowed to continue PRO 140 with existing OBT regimen while waiting for new regimen to be constructed by the Investigator.

- Develops AIDS-defining conditions as specified in Appendix I ([Section 16.1](#)) under which subject is unable to continue treatment with study drug (PRO 140), or subject require treatment with prohibited concomitant medications.
- Shows signs or symptoms of clinically significant immunosuppression
- Subject or the subject's clinician wishes to adjust OBT (except in the event of toxicity management).
- Subject becomes pregnant.

5.2.2 Data Collected for Withdrawn Subjects

Patients may withdraw from the study or discontinue study treatment at any time; however, CytoDyn is dedicated to minimizing missing data in this study. It is therefore suggested that all patients, regardless of whether they continue to receive study treatment, continue within the study.

Investigators considering discontinuing study treatment should contact the medical monitor prior to such discontinuation. Patients who have study treatment discontinued will continue to be followed, per protocol, whenever possible. Patients who have study treatment discontinued due to a serious adverse event will be followed until resolution or stabilization of the event.

In the event that a subject is withdrawn from the study at any time due to an adverse event or serious adverse event (SAE), the procedures stated in [Section 9.1.1](#) or [9.3](#), respectively must be followed.

Every attempt should be made to collect follow-up information. The reason for withdrawal from the study will be recorded in the source documents and on the appropriate page of the eCRF.

Before a subject is identified as lost-to-follow up, the site should make all reasonable efforts to contact the subject. These attempts must be documented and should include at a minimum one phone call and one certified letter.

5.3 SCREEN FAILURES

A subject who has signed a consent form, has been assigned a screening number, but is not treated is classified as a screen failure. Subject number, demographics and reason for screen failure will be recorded.

6 STUDY TREATMENT

6.1 INVESTIGATIONAL PRODUCT DESCRIPTION

PRO 140 is a humanized IgG4,κ monoclonal antibody (mAb) to the chemokine receptor CCR5. PRO 140 is provided at a concentration of 175 mg/mL and is intended for SC route of administration.

Kits will be labeled with a unique identification number. Each kit used during Part 1 and Part 2 of the Treatment Phase will contain two vials of PRO 140 for SC injection. One milliliter (1 mL) of PRO 140 solution will be drawn from each vial and loaded into the syringe. A total of 700 mg (175 mg/mL) of PRO 140 is delivered as two 2 mL injections administered subcutaneously on opposite sides of the abdomen. One study injection kit will be assigned per subject per treatment visit.

Each vial of the PRO 140 product contains ~1.4 mL antibody at 175mg/ml in a buffer containing 5 mM L-histidine, 15.0 mM glycine, 95 mM sodium chloride, 0.3% (w/v) sorbitol, 0.005% (w/v) polysorbate 20 (Tween 20®), and sterile water for injection, at pH of 5.5.

Note: 1 mL injection will be drawn from 1.4 mL solution in a vial. Remaining 0.4 mL medication will be discarded appropriately from each vial.

Table 6-1 and **Table 6-2** provide the unit strength, dosing frequency and mode of administration for the study drug.

Table 6-1: Investigational Product - PRO 140 at T1 visit

Study Drug	Dosage Form	IP concentration	Dosing Frequency and Amount	Route of Administration
PRO 140	Parenteral solution	175 mg/mL	2 injections of PRO 140 (2 X 2mL/inj.) per week on opposite sides of abdomen at T1 visit	SC injection

Table 6-2: Investigational Product - PRO 140 at T2 - T25 visit

Study Drug	Dosage Form	IP concentration	Dosing Frequency and Amount	Route of Administration
PRO 140	Parenteral solution	175 mg/mL	2 injections of PRO 140 (2 X 2mL/inj.) per week on opposite sides of abdomen for up to 24 weeks (T2 – T25)	SC injection

Note: Patients with low body fat percentages may find subcutaneous injections uncomfortable. In such cases, PRO 140 700 mg can be injected as four 175mg/ml injections of 1 mL each and/or can be placed at different areas other than abdomen as per discretion of the Investigator.

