6.2 INVESTIGATIONAL PRODUCT PACKAGING AND LABELING

Study drug will be prepared by Ajinomoto Althea, Inc. and will be packaged, labeled, and shipped by Sherpa Clinical Packaging, LLC.

The contents of each vial are described in [Section 6.1](#). PRO 140 kits will be labeled with information such as: study protocol #; fill volume; concentration; storage condition; a “use as per study protocol” statement; a cautionary statement; sponsor’s name and address; and the kit number.

Below are representative samples of the Investigational Product, Fixed Dose Procedure (FDP) individual vial (

[Figure 6-1](#)), syringe label ([Figure 6-2](#)), and kit labels ([Figure 6-3](#)) designated for use in this clinical protocol. Each kit contains two labeled vials and two syringe labels.

Figure 6-1: Investigational Product - Vial Label

Part 1: One-week treatment period (T1)

Protocol: PRO 140_CD02	Kit No. xxx	Protocol: PRO 140_CD02	Kit No. xxx
Subject No. _____		Subject No. _____	
Single use 3 mL vial contains 1.4 mL of PRO 140 (175 mg/mL) solution for subcutaneous injection		Single use 3 mL vial contains 1.4 mL of PRO 140 (175 mg/mL) solution for subcutaneous injection	
Store at 2°C to 8°C (36°F to 46°F)		Store at 2°C to 8°C (36°F to 46°F)	
USE AS PER STUDY PROTOCOL		USE AS PER STUDY PROTOCOL	
Caution: New Drug – Limited by Federal (or United States) Law to Investigational Use		Caution: New Drug – Limited by Federal (or United States) Law to Investigational Use	
CytoDyn Inc., Vancouver, WA, USA		CytoDyn Inc., Vancouver, WA, USA	

Part 2: 24-week treatment period (T2 – T25)

Protocol: PRO 140_CD02	Kit No. xxx	Protocol: PRO 140_CD02	Kit No. xxx
Subject No. _____		Subject No. _____	
Single use 3 mL vial contains 1.4 mL of PRO 140 (175 mg/mL) solution for subcutaneous injection		Single use 3 mL vial contains 1.4 mL of PRO 140 (175 mg/mL) solution for subcutaneous injection	
Store at 2°C to 8°C (36°F to 46°F)		Store at 2°C to 8°C (36°F to 46°F)	
USE AS PER STUDY PROTOCOL		USE AS PER STUDY PROTOCOL	
Caution: New Drug – Limited by Federal (or United States) Law to Investigational Use		Caution: New Drug – Limited by Federal (or United States) Law to Investigational Use	
CytoDyn Inc., Vancouver, WA, USA		CytoDyn Inc., Vancouver, WA, USA	

Figure 6-2: Investigational Product - Syringe Label**Part 1: One-week treatment period (T1)**

Protocol: PRO 140_CD02	Contents of Kit No. xxx
This syringe contains 1 mL PRO 140 (175 mg/mL) solution for subcutaneous injection	

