USE AS PER STUDY PROTOCOL	
Caution: New Drug – Limited by Federal (or United States) Law to Investigational Use	
CytoDyn Inc., Vancouver, WA, USA	

Part 2: 24-week treatment period (T2 – T25)

Protocol: PRO 140_CD02	Contents of Kit No. xxx
This syringe contains 1 mL PRO 140 (175 mg/mL) solution for subcutaneous injection	
USE AS PER STUDY PROTOCOL	
Caution: New Drug – Limited by Federal (or United States) Law to Investigational Use	
CytoDyn Inc., Vancouver, WA, USA	

Figure 6-3: Investigational Product - Kit Label**Part 1: One-week treatment period (T1)**

Protocol: PRO 140_CD02	Kit No. xxx
Site No. _____	Subject No. _____
This kit contains 2 single-use vials	
Each 3 mL vial contains 1.4 mL of PRO 140 (175 mg/mL) solution for subcutaneous injection	
Store at 2°C to 8°C (36°F to 46°F)	
USE AS PER STUDY PROTOCOL	
Caution: New Drug – Limited by Federal (or United States) Law to Investigational Use	
CytoDyn Inc., Vancouver, WA, USA	

Part 2: 24-week treatment period (T2 – T25)

Protocol: PRO 140_CD02	Kit No. xxx
Site No. _____	Subject No. _____
This kit contains 2 single-use vials	
Each 3 mL vial contains 1.4 mL of PRO 140 (175 mg/mL) solution for subcutaneous injection	
Store at 2°C to 8°C (36°F to 46°F)	
USE AS PER STUDY PROTOCOL	
Caution: New Drug – Limited by Federal (or United States) Law to Investigational Use	
CytoDyn Inc., Vancouver, WA, USA	

The pharmacy manual provides the criteria regarding vial acceptance or rejection, as well as instructions for the preparation of the IP syringes to be used to administer drug.

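### The kit and preparation instructions supply 350 mg per visit (490 mg at most), but the protocol dose for new subjects is 700 mg, including the T1 dose behind the primary endpoint

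*Protocol*

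**What the plan says.** **Dose.** The synopsis, Section 4.3 and Tables 0-1, 0-2, 4-3, 4-4, 6-1 and 6-2 set 700 mg, or the equivalent two injections of 2 mL at 175 mg/mL, at T1 and weekly from T2 to T25. Section 6.1 repeats it: "A total of 700 mg (175 mg/mL) of PRO 140 is delivered as two 2 mL injections". For subjects with low body fat, Sections 6.1 and 6.4 add that "PRO 140 700 mg can be injected as four 175mg/ml injections of 1 mL each". The only subjects for whom 350 mg is mentioned as a dose in this trial's treatment plan are those already enrolled on it, who may move to 700 mg (synopsis and Section 3).

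**Supply and preparation.**
- Section 6.1, immediately before the 700 mg sentence: "One milliliter (1 mL) of PRO 140 solution will be drawn from each vial and loaded into the syringe".
- Section 6.1, on kits: "One study injection kit will be assigned per subject per treatment visit". The same section puts two vials in each kit used in Parts 1 and 2.
- Section 6.1, on the residue: "Remaining 0.4 mL medication will be discarded appropriately from each vial".
- Section 6.2: "Each kit contains two labeled vials and two syringe labels". The kit label reads "Each 3 mL vial contains 1.4 mL of PRO 140 (175 mg/mL) solution for subcutaneous injection", and the syringe label for both parts reads "This syringe contains 1 mL PRO 140 (175 mg/mL) solution for subcutaneous injection".
- Section 6.4 has two syringes, each filled to deliver 1.0 mL.
- Section 4.3.1, the T1 instruction, has two injections of 1 mL.

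**The concern.** The dose statements and the handling statements describe different doses, and both stand in the current text without anything to separate them. In Section 6.1 they are adjacent sentences of one paragraph. A site that follows the draw volume, the syringe fill, the label and the T1 instruction gives half the stated dose. A site that follows the dose tables cannot do so from the one kit it is assigned.

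Two features make this more than untidy wording. First, the primary endpoint is the proportion of subjects with at least a 0.5 log10 fall in viral load at the end of the first week, after the single T1 dose. Section 4.3.1, which governs that visit, is one of the places that gives the 350 mg version. Second, Section 1.5 explains the move to 700 mg by suspected inadequate dosing at 350 mg. If the preparation text is followed, subjects receive the dose the sponsor meant to leave behind while the protocol reports 700 mg.

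**Working it through.** Dose is volume multiplied by concentration. All inputs are in the protocol: 175 mg/mL; about 1.4 mL per vial; two vials per kit; one kit per visit; 1 mL drawn per vial (Sections 6.1 and 6.2); two 2 mL injections per visit (Tables 4-3, 4-4, 6-1 and 6-2).

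**1. The protocol's own figure.** 2 × 2 mL × 175 mg/mL = 700 mg. The low-body-fat variant agrees: 4 × 1 mL × 175 mg/mL = 700 mg. Both need 4.0 mL.

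**2. What the preparation text gives.** 1 kit × 2 vials × 1 mL × 175 mg/mL = 350 mg, from 2.0 mL. The share is 350/700 = 50%.

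**3. The most one kit can hold.** Ignore the discard rule and empty both vials: 2 × 1.4 mL = 2.8 mL, and 2.8 × 175 = 490 mg. The share is 490/700 = 70%. The shortfall is 4.0 − 2.8 = 1.2 mL, or 1.2 × 175 = 210 mg. One 2 mL injection cannot be drawn from one 1.4 mL vial.

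**4. What 700 mg needs.** At 1 mL per vial, 4.0/1.0 = 4 vials, or two kits. With vials emptied completely, 4.0/1.4 = 2.86, so 3 vials, which still means opening two kits. Two vials are enough only if each yields at least 2 mL.

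| Reading | Volume per visit | Dose | Share of 700 mg |
|---|---|---|---|
| Dose tables | 4.0 mL | 700 mg | 100% |
| Preparation text, labels, T1 instruction | 2.0 mL | 350 mg | 50% |
| One kit, both vials emptied | 2.8 mL | 490 mg | 70% |

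**5. Supply over the trial.** For a subject who receives all 25 doses, two kits per visit is 25 × 2 = 50 kits, against the 25 × 1 = 25 that Section 6.1 assigns.

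**6. Could the 350 mg text be meant only for subjects already on 350 mg?** Nothing says so. Section 6.1 describes the kits for both treatment parts and names 700 mg in the same paragraph, Section 4.3.1 carries no restriction by dose, and no separate 700 mg kit is described.

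**The case against.** The best reply is that nobody can doubt the intended dose. It is 700 mg throughout the synopsis, the treatment section and the dose tables, and the 1 mL wording looks like carry-over from the time the trial dosed 350 mg. The sample labels bear the number of the preceding CD02 study, which used 350 mg, so they may say little about what was shipped. Sections 6.2 and 6.4 send sites to a pharmacy manual that may have the preparation right. On consequences, Section 1.5 expects 350 mg to reach the Emax plateau, and its worry about underdosing comes from long-term monotherapy, not from one week added to a failing regimen. The trial is single-arm and descriptive, with no success threshold, so no error rate is affected.

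Much of this stands, but none of it removes the contradiction:
- Carry-over probably explains the conflict, yet it runs through four sections, one of them the T1 instruction.
- Section 6.2 presents the labels as meant for this protocol, and the prose conflicts without them.
- A correct pharmacy manual would have to contradict the protocol's kit count, draw volume and syringe fill, while the labels tell staff to follow the protocol.
- The points about the one-week response and the absence of a test are fair. The case for correction rests on dosing accuracy and known exposure, not on a demonstrated bias.

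**Conclusion.** The concern holds and must be corrected. As written, the preparation and T1 instructions deliver 350 mg, half the protocol dose, and no reading of the kit text gets beyond 490 mg from the one kit assigned to a visit. The result is simple arithmetic on figures in the protocol. It assumes only that vials hold their nominal 1.4 mL (Section 6.1 says approximately) and that kits are as described.

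Two things are not known. The pharmacy manual is not available, and the protocol cannot show what any site actually injected. The effect on the week-1 response is not quantified, and given the Emax argument in Section 1.5 it may be small or nil.

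**What to change.** Amend Sections 4.3.1, 6.1, 6.2 and 6.4 and the vial, syringe and kit labels so that each visit supplies 4.0 mL. Either of two routes works:

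- **Keep the present vial.** Use four vials per visit (two current kits), drawing 1 mL from each, given as two 2 mL syringes or four 1 mL injections.
- **Change the vial.** Use two vials that each yield at least 2 mL, with 2 mL syringe fills and matching labels.

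State the number of kits per visit to match, align the pharmacy manual, and update the sentence in Section 1.5 that still describes 350 mg weekly dosing as the plan for this study. As an optional addition, since some enrolled subjects started on 350 mg, tabulate the week-1 endpoints by the dose actually injected at T1 if the SAP does not already do so.

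The first route costs text and label corrections and twice the kits. The second adds a change in manufacture and supply, whose feasibility the protocol does not show. The 700 mg dose already implies at least the injected volume of drug, and design, visits and endpoints are unchanged.

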6.2 INVESTIGATIONAL PRODUCT PACKAGING AND LABELING

Study drug will be prepared by Ajinomoto Althea, Inc. and will be packaged, labeled, and shipped by Sherpa Clinical Packaging, LLC.

The contents of each vial are described in [Section 6.1](#). PRO 140 kits will be labeled with information such as: study protocol #; fill volume; concentration; storage condition; a “use as per study protocol” statement; a cautionary statement; sponsor’s name and address; and the kit number.

Below are representative samples of the Investigational Product, Fixed Dose Procedure (FDP) individual vial (

[Figure 6-1](#)), syringe label ([Figure 6-2](#)), and kit labels ([Figure 6-3](#)) designated for use in this clinical protocol. Each kit contains two labeled vials and two syringe labels.

Figure 6-1: Investigational Product - Vial Label

Part 1: One-week treatment period (T1)

Protocol: PRO 140_CD02	Kit No. xxx	Protocol: PRO 140_CD02	Kit No. xxx
Subject No. _____		Subject No. _____	
Single use 3 mL vial contains 1.4 mL of PRO 140 (175 mg/mL) solution for subcutaneous injection		Single use 3 mL vial contains 1.4 mL of PRO 140 (175 mg/mL) solution for subcutaneous injection	
Store at 2°C to 8°C (36°F to 46°F)		Store at 2°C to 8°C (36°F to 46°F)	
USE AS PER STUDY PROTOCOL		USE AS PER STUDY PROTOCOL	
Caution: New Drug – Limited by Federal (or United States) Law to Investigational Use		Caution: New Drug – Limited by Federal (or United States) Law to Investigational Use	
CytoDyn Inc., Vancouver, WA, USA		CytoDyn Inc., Vancouver, WA, USA	

Part 2: 24-week treatment period (T2 – T25)

Protocol: PRO 140_CD02	Kit No. xxx	Protocol: PRO 140_CD02	Kit No. xxx
Subject No. _____		Subject No. _____	
Single use 3 mL vial contains 1.4 mL of PRO 140 (175 mg/mL) solution for subcutaneous injection		Single use 3 mL vial contains 1.4 mL of PRO 140 (175 mg/mL) solution for subcutaneous injection	
Store at 2°C to 8°C (36°F to 46°F)		Store at 2°C to 8°C (36°F to 46°F)	
USE AS PER STUDY PROTOCOL		USE AS PER STUDY PROTOCOL	
Caution: New Drug – Limited by Federal (or United States) Law to Investigational Use		Caution: New Drug – Limited by Federal (or United States) Law to Investigational Use	
CytoDyn Inc., Vancouver, WA, USA		CytoDyn Inc., Vancouver, WA, USA	

Figure 6-2: Investigational Product - Syringe Label**Part 1: One-week treatment period (T1)**

Protocol: PRO 140_CD02	Contents of Kit No. xxx
This syringe contains 1 mL PRO 140 (175 mg/mL) solution for subcutaneous injection	
USE AS PER STUDY PROTOCOL	
Caution: New Drug – Limited by Federal (or United States) Law to Investigational Use	
CytoDyn Inc., Vancouver, WA, USA	

Part 2: 24-week treatment period (T2 – T25)

Protocol: PRO 140_CD02	Contents of Kit No. xxx
This syringe contains 1 mL PRO 140 (175 mg/mL) solution for subcutaneous injection	
USE AS PER STUDY PROTOCOL	
Caution: New Drug – Limited by Federal (or United States) Law to Investigational Use	
CytoDyn Inc., Vancouver, WA, USA	

Figure 6-3: Investigational Product - Kit Label**Part 1: One-week treatment period (T1)**

Protocol: PRO 140_CD02	Kit No. xxx
Site No. _____	Subject No. _____
This kit contains 2 single-use vials	
Each 3 mL vial contains 1.4 mL of PRO 140 (175 mg/mL) solution for subcutaneous injection	
Store at 2°C to 8°C (36°F to 46°F)	
USE AS PER STUDY PROTOCOL	
Caution: New Drug – Limited by Federal (or United States) Law to Investigational Use	
CytoDyn Inc., Vancouver, WA, USA	

Part 2: 24-week treatment period (T2 – T25)

Protocol: PRO 140_CD02	Kit No. xxx
Site No. _____	Subject No. _____
This kit contains 2 single-use vials	
Each 3 mL vial contains 1.4 mL of PRO 140 (175 mg/mL) solution for subcutaneous injection	
Store at 2°C to 8°C (36°F to 46°F)	
USE AS PER STUDY PROTOCOL	
Caution: New Drug – Limited by Federal (or United States) Law to Investigational Use	
CytoDyn Inc., Vancouver, WA, USA	

The pharmacy manual provides the criteria regarding vial acceptance or rejection, as well as instructions for the preparation of the IP syringes to be used to administer drug.

